Hypothesis: Loteprednol 0.5% gel will perform similarly or better than a regimen of prednisolone acetate 1% and fluorometholone 0.1% in the prevention of visually significant postoperative corneal haze after photorefractive keratectomy (PRK) with a lower incidence of intraocular pressure elevation.

Objectives: We aim to conduct a prospective, randomized trial to compare the incidence of intraocular pressure rise and visually significant postoperative corneal haze after PRK with the use of loteprednol 0.5% gel compared to the use of earlier generation steroids, prednisolone acetate 1% suspension and fluorometholone 0.1% suspension.

Patients undergoing PRK will be assigned to 1 of 2 postoperative steroid regimens. Group 1 will use only loteprednol 0.5% gel, tapered off slowly based on clinical evaluations of the corneal healing response. Group 2 will use prednisolone acetate 1% suspension tapered down to a regimen of fluorometholone 0.1% which will then be tapered off based on clinical evaluations of the corneal healing response. If no difference in efficacy or safety is detected between these two regimens, this study will support the use of either steroid regimen in patients after PRK. If there is a major difference in the efficacy or safety of these two regimens, this could influence post-refractive surgery treatment practices.

7. Is this a multi-site study, where more than one site needs IRB approval?

Yes No

8. Background and Introduction:

In photo-ablation procedures, an excimer laser is used to sculpt corneal tissue to correct refractive error. During PRK, the surface epithelium is removed and the laser energy is applied to reshape the underlying corneal stroma. This procedure is FDA approved and used widely. Corneal haze is a well known and a potentially vision threatening postoperative complication of PRK. Topical ophthalmic corticosteroids are routinely prescribed by most surgeons postoperatively to help prevent this complication.

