Prior to surgery, patients will be randomly assigned to one of two postoperative steroid regimens. Group 1 will use loteprednol 0.5% gel in both eyes, starting at a frequency of four times per day for the first week and then tapered off based on clinical judgement of the corneal healing response. Group 2 will use prednisolone acetate 1% suspension in both eyes, starting at a frequency of four times per day for the first week, then tapered down to a regimen of fluorometholone 0.1% suspension, which will then be tapered off based on clinical judgement of the corneal healing response.

All surgical procedures will be performed according to the standard of care and the surgeons' standard practices. The study outcome measures are standard of care for pre-operative and post-operative evaluation of refractive surgery patients.

The primary outcome measure will be intraocular pressure at each study time point. Secondary outcomes will be grade of corneal haze, manifest refraction, best corrected visual acuity, and uncorrected visual acuity.

Study outcome measures will be evaluated for each treated eye of each subject at each study time point. Routine clinical management may be altered if the intraocular pressure is elevated sufficiently to require medical intervention, if there is significant postoperative corneal haze, or if there are other postoperative complications. In these situations, additional IOP lowering drops may be added or the steroid decreased, changed, or increased, based on the clinical picture and physician judgement. Additional examinations between study time points may be performed as necessary according to the surgeon's usual care, but will not be considered part of the study data. Patients have the right to withdraw at any time and future medical care will not be influenced by their lack of participation.

If enhancement surgery is deemed necessary and performed during the one-year post-operative period, study data collection will end for that eye at the time of the enhancement. All prior data collected will still be included in the statistical analysis and if only one eye requires enhancement, data collection will continue on the fellow eye until the last planned study time point.

Eyes will be evaluated with the following procedures:

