Yes No

If no, list the procedures that are performed for research purposes only (non-standard or non-standard of care procedures):

Only data collection and analysis are for research purposes only. All other procedures are within the standard of care.

8. Is there a safety monitoring plan for this study?

Yes No

9. Provide a summary of the statistical methods, data analysis, or data interpretation planned for this study. Factors for determining the proposed sample size (e.g., power) should be stated.

Standard statistics will be calculated and used to describe the two treatment groups in terms of all study variables: intraocular pressure, grade of corneal haze, manifest refraction, best corrected visual acuity, and uncorrected visual acuity. Statistics will be compiled for each variable at the study time points listed in the data collection protocol. Patients withdrawn from the study prior to surgery will not be included in the data analysis and will be replaced in the enrollment group. For eyes that require enhancement surgery, only data collected prior to the enhancement surgery will be included in the statistical analysis.

Prior studies have considered intraocular pressure elevation of greater than or equal to 10 mm Hg above baseline clinically significant. A prior study of healthy volunteers demonstrated an incidence of IOP elevation > 10 mm Hg of 1.95% in patients using loteprednol eye drops versus 7.48% in patients using dexamethasone eye drops [1]. Using these expected proportions, an alpha of 0.05, and a power of 80%, we would need a sample size of 230 patients (460 eyes). In order to account for about 10% dropout, we intend to enroll 250 patients in the study, 125 in the loteprednol arm and 125 in the prednisolone and fluorometholone arm.

IRB_00075978

Created: 8/9/2014 9:53 AM

IRB_00075978

PI: [name]

Submitted: 8/20/2014

View: 4.2 Consent Process

Title: Efficacy and safety of loteprednol 0.5% gel for routine prophylaxis after photorefractive keratectomy compared to prednisolone acetate 1% suspension and fluorometholone 0.1% suspension

Consent Process

1. The following investigators and internal staff will obtain consent (as indicated on the Study Location and Sponsors Page):

[name] University of Utah

[name]

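### The objective is an incidence of IOP rise and haze over follow-up, but the plan only summarises visit by visit and has no rule for patients who leave after surgery, so no planned summary estimates that incidence

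*Combined protocol and SAP*

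**What the plan says.** The Objectives set out to "compare the incidence of intraocular pressure rise and visually significant postoperative corneal haze after PRK". Item 6 of section 4 makes IOP at every study visit the primary outcome, with haze among the secondary outcomes. IOP is read before surgery, at week 1 and at months 1, 2, 3, 6 and 12; haze is graded from month 1 to month 12.

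Item 9 describes the analysis as descriptive statistics for the two groups: "Statistics will be compiled for each variable at the study time points listed in the data collection protocol". It names no between-arm test, analysis population, imputation, model for partial follow-up or sensitivity analysis.

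Two exits have an analysis rule. The first is "Patients withdrawn from the study prior to surgery will not be included in the data analysis and will be replaced in the enrollment group". The second is enhancement surgery: data collection ends for that eye, earlier data are kept, and the fellow eye continues. Item 6 also says "Patients have the right to withdraw at any time and future medical care will not be influenced by their lack of participation", and patients discontinued for an adverse event are asked back for a final evaluation. Neither of these statements says how the patient is counted.

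The sample size in item 9 uses an incidence of IOP elevation of "1.95% in patients using loteprednol eye drops versus 7.48% in patients using dexamethasone eye drops", with "an alpha of 0.05, and a power of 80"%. It arrives at 230 patients (460 eyes), and then: "In order to account for about 10% dropout, we intend to enroll 250 patients in the study".

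**The concern.** The question and the analysis do not match. An incidence over follow-up counts each operated patient (or eye) once: did a rise occur at any reading or not? A series of visit summaries has a different denominator at each visit, made up of whoever attended. A patient with a rise at month 1 who then leaves contributes an event at month 1 and nothing later. A patient who leaves without a rise contributes a non-event at the early visits and is then absent. The visit figures cannot be added up into an incidence, and the plan does not say how they would be combined.

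This matters because the events are few and the expected leavers are not. There are also reasons not to take balanced, uninformative dropout for granted. Patients are not described as masked, and section 6 says that loteprednol is supplied free while control patients pay for their drops. A diluted difference would be read as support for either regimen, because that is how the plan says it will interpret finding no difference.

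**Working it through.** **Inputs, all from item 9:** event rates 1.95% (loteprednol) and 7.48% (taken from dexamethasone); alpha 0.05; power 80%; 230 patients required; about 10% dropout; 250 enrolled, 125 per arm. Sidedness is not stated. I assume two-sided, because that reproduces the plan's figure.

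**Step 1. Reproduce the plan's number.** Pooled two-proportion formula, no continuity correction, with mean rate 0.04715 and difference 0.0553:

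n per arm = [1.96 × √(2 × 0.04715 × 0.95285) + 0.8416 × √(0.0195 × 0.9805 + 0.0748 × 0.9252)]² / 0.0553²

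= (0.5875 + 0.2501)² / 0.003058 = 229.4, so 230 per arm and 460 in total.

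The plan's 460 is therefore reproduced in eyes, with each eye treated as independent.

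**Step 2. Leavers against events.** Withdrawals before surgery are replaced, so the 10% allowance is sensibly read as loss after surgery. That is an inference.

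| Unit | Leavers | Expected events, full enrolment | Expected events, 90% remaining |
|---|---|---|---|
| Patients | 250 × 0.10 = 25 | 125 × 0.0195 + 125 × 0.0748 = 2.4 + 9.4 = 11.8 | 112.5 × 0.0943 = 10.6 |
| Eyes | 50 | 250 × 0.0943 = 23.6 | 225 × 0.0943 = 21.2 |

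Leavers are about twice the events on either count.

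**Step 3. How far an unwritten choice could reach.** Assume 13 leavers per arm and 2 v 8 events seen:
- all leavers scored as non-events: 2/125 v 8/125 = 1.6% v 6.4%
- only control leavers scored as events: 2/125 v 21/125 = 1.6% v 16.8%
- only loteprednol leavers scored as events: 15/125 v 8/125 = 12.0% v 6.4%

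These are outer bounds, not forecasts.

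**Step 4. A less extreme case.** Assume 10% leave each arm, leavers have k times the stayers' event rate, and power is taken on the plan's own eye-level formula. The stayers' rate is p / (0.9 + 0.1k).

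| k (assumed) | No leaver's event seen, leavers excluded (225 eyes per arm) | Half of leavers' events seen, leavers kept (250 eyes per arm) |
|---|---|---|
| 2 | 75% | 79% |
| 3 | 71% | 78% |
| 5 | 64% | 75% |

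The documents give no value for k or for the share of events seen. The gap between the columns shows that keeping leavers and their readings recovers much of the loss.

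**Step 5. The dropout arithmetic.** 250 × 0.90 = 225, which is 5 short of 230. 230 / 0.90 = 255.6, so 256 would be needed. 1 − 230/250 = 8%. On the eye-level formula, power is 80.1% at 230 per arm and 79.2% at 225.

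**Step 6. The unit.** If the stated rates apply per patient and each patient is scored once, the same formula gives about 51% power at 115 per arm.

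**The case against.** The strongest reply is that the primary outcome is an IOP value at each visit, so visit summaries are what it calls for. The rise of 10 mm Hg appears only in the sample-size paragraph, with no test attached; the missing dropout rule is then a by-product of a larger omission. That is fair as to cause. It does not supply an analysis for the incidence that the Objectives name and the sample size is built on.

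Three stronger readings are tempting and should not be drawn.

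- A reader might infer that leavers' data are discarded or that leavers are scored nowhere. The documents do not say so. A leaver counts at every visit attended, no earlier reading is said to be dropped, and the one comparable exit (enhancement) keeps prior data.
- A reader might infer that dropout will bias the result or sink the power. Nothing in the documents sets the size or direction of informative dropout. IOP is read six times after surgery, so many leavers will have readings. IOP and haze assessors are masked, and all participants have a reduced fee that covers examinations to one year.
- A reader might infer that 225 against 230 is a material shortfall. The plan says about 10%, and the loss is under one power point.

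**Conclusion.** The concern holds in this form: the planned visit summaries do not estimate the incidence of IOP rise or haze over follow-up among operated, randomised patients, and leaving after surgery, which the plan expects in about 25 of 250 patients, has no counting rule. Set against roughly 11 to 12 patient-level events, that choice is large enough to matter, and it should be fixed before outcomes by arm are seen. This rests on the plan's own rates and on reading the 10% as loss after surgery. The size of any bias cannot be stated from the documents; Steps 3 and 4 show only what is possible under labelled assumptions. The 225/230 mismatch is a wording correction.

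**What to change.** In item 9:

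1. Keep every randomised, operated patient. Define an IOP rise as at least 10 mm Hg above baseline at any study reading up to withdrawal or, for an eye with enhancement, up to the enhancement. Compare arms by time to first rise, censoring event-free leavers at their last reading. Either handle the two eyes as clustered or score once per patient, and say which. Treat visually significant haze the same way, with its grade threshold stated.
2. Analyse IOP values with one repeated-measures mixed model that uses all readings up to withdrawal and accounts for both eyes.
3. Report post-surgery withdrawals by arm, with one sensitivity analysis for informative dropout. This is needed because the censoring in (1) assumes that dropout is uninformative.
4. Restate the dropout allowance as about 8%, which leaves 230 of 250. Do not write in 79% power for 225 patients: that figure holds only if eyes are independent.

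No new visits, measurements or patients are needed. The cost is a little more analysis and a less favourable power statement. A clustered or patient-level analysis will show less than the stated 80%: about 51% at 115 per arm if the stated rates apply per patient. The either-eye rate and the between-eye correlation, which would settle the figure, are not given.
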